3.3.2.1 OXTR DNA methylation from maternal plasma

Methylation will be measured at the University of Arizona's Genetic Core using bisulfite conversion, followed by high-throughput next-generation sequencing of PCR amplicons. Briefly, bisulfite conversion will be performed using the EZ DNA Lightning Kit (Zymo Research, Irvine, CA; D5031). After conversion, DNA will be PCR amplified using previously published primers TSL101F (5'-TTGAGTTTGGATTTAGATAATTAGGATT-3') and TSL101R (5'-biotin-AATAAAATACCTCCACTCCTT ATTCTAA-3').⁽³⁹⁾ These primers amplify a region between -1001 and -856 (relative to the translation start site) allowing us to measure methylation levels of CpG sites at -1001, -959, -934, -924, -901, and -860.⁽³⁸⁾

⁴⁴⁾ Primers will be modified with 5' linker sequences, as previously described,⁽¹⁰⁵⁾ and a two-stage PCR process will be used to incorporate sample-specific barcodes and Illumina sequencing adapters into each amplicon.⁽¹⁰⁶⁾ Deep sequencing (>1000 sequences/amplicon/ sample) of amplicons will be performed using an Illumina MiSeq (Illumina, Inc., San Diego, CA) instrument, and percent methylated cytosine at each position along the OXTR amplicon will be evaluated by analysis of sequence data, allowing for high resolution analysis of percent methylation. Efficacy of bisulfite conversion and sequencing error rates will be evaluated using cytosine positions that are not part of CpG sites, and through methylated and unmethylated standards. Raw reads will be mapped to expected amplicon sequences in a bisulfite conversion-aware manner.⁽¹⁰⁷⁾ Methylation will be quantified at each CpG based on the distribution of methylated and unmethylated bases aligned to that position. Additional exploratory CpG sites have been selected based on their implication in previous studies^(46-50, 69) and cost-effectiveness in co-targeting additional regions using the selected assay.

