4.7 Power Analysis

Our final sample size at the 3-month endpoint is estimated to be at least 100 per treatment arm, after a projected 20% attrition from enrollment of 250 women. This sample size will achieve 80% power to detect as significant a 0.44 standard deviation difference in primary outcomes (M-I synchrony gaze and affect) between treatment arms assuming $\alpha=0.025$ and a 2-sided test. Similar interventions on a related outcome (maternal sensitivity), and preliminary data from members of our team (on OXT level), showed between group effect sizes ranging from 0.28 to 0.62. In addition, the standardized differences in M-I synchrony ranged between 0.12 and 0.7 comparing at-risk (i.e., premature infants, maternal depression) and normal comparison groups at 3 and 9 months, supporting our choice of 0.4 as a feasible and clinically meaningful effect size. For aim 2 we have 80% power to detect modest correlations of 0.22 and larger assuming a conservative $\alpha=0.01$.

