4.8 Statistical Analysis Plan

Our primary statistical approach is regression based, using a general linear model to conduct bivariate correlations, multiple linear regression, analysis of variance or covariance, as well as tests of mediation and/or moderation and a mixed-effect model for repeated measures (MMRM) recommended for primary analysis of clinical trials with continuous endpoints.⁽¹³⁶⁾ We will screen measures for violations of assumptions and use robust standard errors or power transformations if assumptions are not met. All regression-based analyses will be performed using either SAS software, version 9.4 (SAS Institute Inc., Cary, NC), or Stata, version 15.1⁽¹³⁷⁾ We will also adopt a discovery-based analysis of patient sub-groupings. This analysis will be based on an unsupervised clustering of all patients across all molecular measurements, with two primary outcomes. We will identify (1) patterns of molecular expression linking different

methylation profiles to gene and protein expression to evaluate the types of molecular signatures that discriminate sample groupings, and (2) sets of clinical covariates that are associated with sample sub-groups to determine the clinical and phenotypic factors that describe and differentiate sample clusters. These analyses will be performed using R software.

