
4.8.2 Identify OXT-System Mechanisms Associated with M-I Synchrony

Aim 2: Identify molecular mechanisms in the OXT system underlying M-I synchrony. We will examine the time change pattern of OXT elements to understand the form of their trajectory (e.g., ascending or descending, linear, quadratic) using locally weighted regression (lowess) graphs, stratified by treatment arm. We will also assess the form of hypothesized relationships between elements (i.e., *OXTR* methylation negatively related to *OXTR* mRNA, OXTR protein, and OXT peptide - which are positively related to each other) stratified by treatment group and time. We will model these time change patterns with MMRM and use interactions of time, intervention, and the OXT element to establish if aspects of the OXT system and/or their interrelationships change over time and if that change is influenced by the ATVV intervention. Ultimately, we will assess if the behavioral measure of M-I synchrony is associated with the OXT system and its components, including methylation at base pairs and time trends across repeated measurements. We will examine covariates such as childhood adversity and cumulative stress for their substantive contribution to understanding the relationship between M-I synchrony and OXT functioning, including effect modification with interaction terms. While we will test for heterogeneity in random coefficients through MMRM, we will further explore population heterogeneity using bioinformatics methods, described below, which will provide a complementary, person-centered approach to understanding how subgroups inferred from the OXT indicators are related to personal characteristics, dose, and outcomes.

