Molecular Profiles: To address heterogeneity in molecular profiles we will perform a clustering analysis to identify potential subgroups with differing patterns of associations within the OXT system. We will use k-means clustering, doing a search for the optimal number of clusters k by repeating clustering several times for each k over a wide range and using consensus clustering statistics to determine the values of k that yield highly reproducible clustering results. This will yield sample sub-groups that faithfully capture the heterogeneity in the data set without over-fitting clusters to noise. We can then profile the subgroups using the key covariates, treatment arm, and M-I synchrony using descriptive and bivariate inferential statistics. In addition, we can examine the different molecular profiles that discriminate different sub-populations to determine putative molecular mechanisms linked to different outcomes observed in the covariate analysis. We will evaluate such differences both qualitatively, using heatmap visualizations, and quantitatively, based on differences between cluster centroids. This will allow us to generate hypotheses about biomarkers that might distinguish individuals most likely to benefit from the intervention. These combined methods will inform us about the efficacy of the ATVV intervention, increase our understanding of the OXT system associated with M-I synchrony, and support our future research to enhance targeted or tailored intervention efforts.

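### The molecular-subgroup rule selects k by reproducibility alone, with no cut-off or one-population reference, so the promised protection against clustering noise is not established

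*Combined protocol and SAP*

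**What the plan says.** Section 4.8.2 (Molecular Profiles) plans k-means clustering of the oxytocin (OXT) measurements to "identify potential subgroups with differing patterns of associations within the OXT system". The number of clusters is to be found by "doing a search for the optimal number of clusters k by repeating clustering several times for each k over a wide range". The criterion for choosing among the candidate values is given as "using consensus clustering statistics to determine the values of k that yield highly reproducible clustering results". The next sentence draws the conclusion: "This will yield sample sub-groups that faithfully capture the heterogeneity in the data set without over-fitting clusters to noise".

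Section 4.8 defines what is clustered: "This analysis will be based on an unsupervised clustering of all patients across all molecular measurements, with two primary outcomes". The two outcomes meant there are products of the cluster analysis (molecular patterns, and the covariates that go with them), not gaze and affect synchrony.

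The plan does not say which consensus statistic is used, what range of k is searched, what level of reproducibility is high enough, or what is reported if there is no structure. It mentions no one-cluster or simulated reference. The clusters are then compared on covariates, treatment arm and synchrony with inferential tests, and on the distances between their centres. They are meant to suggest mechanisms and markers of likely benefit.

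**The concern.** The assurance treats a reproducible partition as a real one. These differ. Where markers are correlated, a single continuous population has a long axis, and k-means with k = 2 tends to cut across it near the middle every time. The result is stable although there are no groups.

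A stability criterion cannot detect this by itself. At k = 1 every pair of participants is always together, so agreement is trivially perfect and k = 1 cannot be ranked against k = 2 or more. The later steps do not expose a false split either, since k-means centres differ by construction.

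At stake is the exploratory part of Aim 2. A split of a continuum could be presented as molecular subtypes and carried into later work on tailoring the intervention.

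**Working it through.** **Plan's own figure.** The plan gives none for the clustering, so there is nothing to reproduce.

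**Inputs from the plan.**
- Sample size: Section 4.7 says "Our final sample size at the 3-month endpoint is estimated to be at least 100 per treatment arm", so n = 2 × 100 = 200.
- Markers: Section 3.3.2.1 gives six sites, "allowing us to measure methylation levels of CpG sites at -1001, -959, -934, -924, -901, and -860". Adding OXTR mRNA, OXTR protein, maternal OXT and infant OXT gives 6 + 4 = 10 variables at month 3.
- Correlation: Section 4.8.2 expects methylation to run against mRNA, protein and peptide, "which are positively related to each other". It gives no sizes.

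**Assumptions.** CpG–CpG correlation is 0, 0.3 or 0.6. All other pairs are 0 in the independent case and 0.1 otherwise. The ARI cut-offs of 0.8 and 0.9 are illustrative.

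**Why correlation matters.** Six variables with common correlation r have leading eigenvalue 1 + 5r. This is 1 + 5 × 0.3 = 2.5 at r = 0.3 and 1 + 5 × 0.6 = 4.0 at r = 0.6, against 1 when independent. The correlated cloud therefore has a dominant axis to cut.

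**Simulation.** Each dataset came from one multivariate normal population with no subgroups, standardised. k-means was run on 80% subsamples. Agreement between partitions was scored by

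ARI = (RI − E[RI]) / (max RI − E[RI]),

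which is 1 for identical partitions and about 0 for chance agreement. The proportion of ambiguous pairs (neither nearly always together nor nearly always apart) was also recorded. Repeated k-means on the full data, the literal reading of the plan's repetition, was scored for k = 2 and 3. There were 60 datasets per row, with k = 2 to 4 under subsampling.

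| CpG r (other pairs) | Mean ARI, k = 2 | Ambiguous pairs, k = 2 | Some k with ARI ≥ 0.8 | Some k with ARI ≥ 0.9 | Full-data repeats, ARI ≥ 0.9 |
|---|---|---|---|---|---|
| 0 (0) | 0.29 | 0.75 | 0% | 0% | 0% |
| 0.3 (0.1) | 0.84 | 0.17 | 70% | 22% | 88% |
| 0.6 (0.1) | 0.88 | 0.13 | 90% | 45% | 100% |

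With 60 datasets the standard error is √(0.70 × 0.30 / 60) = 0.06 for the 70% and √(0.45 × 0.55 / 60) = 0.06 for the 45%.

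**All visits together.** The Schedule of Events gives 9 maternal markers at 4 visits and infant OXT at 3, so 9 × 4 + 3 = 39 variables. A 40-variable version (10 × 4, correlation over time 0.5 or 0.7, only 8 datasets each, k = 2 to 6) gave mean ARI at k = 2 of 0.84 to 0.89, and 75% to 88% of datasets reached 0.8.

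**Does a reference correct it?** Subgroups were declared only if the best consensus ARI (k = 2 or 3) exceeded all 19 values from data simulated from one normal population with the observed covariance. The nominal error is 1/20 = 5%.
- No subgroups: declared in 9/120 = 7.5% at r = 0.3 and 9/120 = 7.5% at r = 0.6. The standard error at 5% is √(0.05 × 0.95 / 120) = 0.020, so each is (0.075 − 0.05) / 0.020 = 1.25 standard errors above nominal.
- Two true equal groups, independent within group: declared in 17/25 = 68% at a separation of 1.5 SD per CpG site and in 24/25 = 96% at 2.0 SD.

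**The case against.** A reader might infer that the rule always takes the most reproducible k and so cannot return a null result. The text does not support that. It asks for highly reproducible values of k, in the plural, and speaks of potential subgroups. Read as an absolute standard, no k might qualify, and with independent markers none would at ARI 0.8. On the other side, the plan also speaks of an optimal k and says without condition that subgroups will result. The null outcome is unstated, not excluded.

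A reader might also infer that clusters will be reported in any homogeneous sample. In a further set of simulations k = 2 was the most stable of k = 2 to 6 in 12 of 12 homogeneous datasets (CpG correlation 0.5, others 0.1). But some k must always rank first, so such counts do not show that a high standard was met. Under a strict cut-off false clustering is less common: with correlated markers, only 2 of 10 datasets per case had fewer than 10% ambiguous pairs.

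Finally, the analysis is labelled as discovery and hypothesis generation. Aim 2's hypothesis is tested by the models in the first part of Section 4.8.2, which treat the OXT elements as continuous whatever the clustering gives. That stands, and it limits the consequence. It does not rescue the assurance sentence, which is an unconditional claim about the method.

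**Conclusion.** The concern holds in limited form. The assurance against clustering noise does not follow from the method described, because reproducibility is the only criterion and nothing compares the result with a single population. At the assumed CpG correlations of 0.3 to 0.6 and n = 200, a homogeneous sample yields a consensus ARI of at least 0.8 in 70% to 90% of cases and at least 0.9 in 22% to 45%. With independent markers the figure at 0.8 is 0%. The size therefore depends on correlations and a cut-off that the plan does not give. The direction depends only on the markers being correlated, which the plan itself predicts.

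The primary outcomes, the randomised comparison and the sample size are untouched. The change is worth making before the clustering is run, but the trial's main conclusions do not depend on it.

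**What to change.** In Section 4.8.2:

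1. Name the consensus statistic and the range of k.
2. Compute the same statistic, with the same search over k, on data simulated from one multivariate normal population with the observed covariance. Alternatively, use a gap statistic that includes k = 1, checked against that reference. Nineteen reference datasets are the fewest that give a 5% rule; 500 would give a steadier threshold. Clearly skewed markers should be transformed first, since skewness alone could exceed a normal reference.
3. Report subgroups only if the observed value exceeds a prespecified upper percentile of the reference, for example the 95th. Otherwise report no evidence of subgroups and rely on the continuous analyses already planned in the same section.
4. Delete or soften the assurance about not over-fitting noise.

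The cost is a little more R analysis and a few lines of text. Some sensitivity to weakly separated groups is lost: in the check above, about a third of datasets (8/25) with true groups 1.5 SD apart per CpG site were not declared. The exploratory analysis may also end with no subgroups to profile.

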5.0 Quality Management

5.1 Primary Outcome: Mother-Infant Synchrony

All M-I dyads will be video recorded freely interacting with each other for 4 minutes (coding occurs on the last 3 minutes). Video recording occurs when the infant is alert and ready to interact, > 30 minutes after the end of a breastfeeding or formula feeding, and data collection order may be adjusted if the baby is sleepy or fussy. As per [name]'s standardized procedure, we will use two cameras on tripods to zoom in on the mother's and infant's faces separately; during coding the software synchronizes the two recordings. To avoid distracting the M-I dyad, research members are outside of the dyad's room and able to view remotely on a laptop the real-time recordings. Later, videos will be coded for M-I synchrony by team members blinded to group assignment. Coders are trained to 90% inter-rater reliability, and 20% of videos will be double coded for inter-rater reliability.

5.1.1 Double Coding Mother-Infant Synchrony Videos

The PI will train (blinded to group assignment) research personnel coding video-recordings for mother-infant synchrony to > 90% inter-rater reliability by the end of their training period. Additionally, a collaborator's laboratory [REDACTED] will provide a service of coding 100% of the study's video recordings for reliability of the mother-infant synchrony measure. Collaborators will follow the UA IRB approved protocol for safe and secure handling of specimens and video recordings labeled with unique anonymous codes. Collaborators will not have access to participant identifiers. Data will be shared using the UA Box Health cloud-based secure system. [REDACTED]

[REDACTED] The University of Arizona will code 20% of the videos for reliability.

5.1.2 Consultation Meetings

5.2 Reliability of ATVV Instruction

The PI is fully trained to criterion (> 90% agreement with the ATVV Reliability Checklist) on the intervention. [REDACTED] will train [REDACTED] to criterion establishing >90% reliability. [REDACTED] will teach the ATVV to

mothers before they are discharged from the hospital after birth. Inter-rater reliability will be periodically measured by [REDACTED] for 20% of videorecorded sessions and maintained above 90%.

5.3 Fidelity of ATVV Methodology

At each study visit (1, 2, and 3 months), we will retest parental reliability (ATVV Reliability Checklist) and instruct mothers how to adapt the ATVV with their maturing infant.

6.0 Data, Safety, & Monitoring Plan

This randomized controlled trial has Institutional Review Board (IRB) approval from the University of Arizona (UA). The risks associated with this study are minimal and the potential for adverse events are low. The proposed study meets the NIH criteria for a phase II clinical trial. The ATVV multisensory massage intervention will occur in 125 mother-infant dyads to primarily determine its efficacy at improving mother-infant interaction, compared to an attention control group of 125 women. While pregnant women, mothers and their healthy full-term infants are vulnerable populations, the infant massage intervention includes behaviors that mother typically use when interacting with their infants and is low risk. For over 30 years, we have applied the ATVV intervention to over 800 infants (who were primarily vulnerable preterm infants) and have never had to terminate the ATVV intervention because of physiologic instability. Data collection methods are also low-risk, involving questionnaires, maternal venipuncture, buccal swab for infant saliva, and a video recording of mother-infant interaction. Additionally, our only contact with pregnant women is for enrollment, and one study visit when they will complete questionnaires and allow collection of one maternal blood sample. Given the low risk of this study, our DSM plan will use a Safety Monitoring Committee (SMC) to allow for an independent committee to review data. According to the Policy of the National Institute of Nursing Research (NINR) for Data and Safety Monitoring of Extramural Clinical Trials, an SMC is “a group of two or more experts, who are independent of the protocol, which reviews data from a particular study.” Generally, one of these experts is a biostatistician.

6.1 Monitoring Entity

The Principal Investigator (PI) holds primary responsibility for data safety and monitoring. The plan includes a SMC with two committee members, outside of the University of Arizona, who are independent from the study protocol, have experience in clinical trials, and do not have conflicting interests. [REDACTED]

6.2 Procedures for Monitoring Study Safety and to Minimize Risk

To promote study safety, there are weekly research team meetings for the initial 6-months, and bi-weekly team meetings after the initial 6-months. Team meetings (with the PI, program coordinator, research assistants, and select co-investigators) includes monitoring of the following items-

- recruitment,
- retention,
- attrition.

- performance of the study site,
- reliability and fidelity of the intervention,
- confidential data collection and data management,
- quality and integrity of data, and
- participant safety.

The research team members identify potential safety issues and solutions.

The SMC meets semiannually to review data safety and monitoring. The SMC will convene more often if necessary. The SMC reviews materials provided to them by the PI on the following –

- study progress,
- study procedures and protocol,
- performance of the study site,
- confidential data collection and data management,
- quality and integrity of data, and
- participant safety.

The SMC conducts an audit of the following –

- randomly selected 25% of participant consent/parental permission forms to assure compliance with IRB requirements;
- randomly selected 25% of participant data records to assure reliability of data entry including assessing all variables that are missing, invalid or inconsistent;
- monthly quality assurance reports; and
- unanticipated problems and adverse events (see 6.4).

6.2.1 PI Responsibilities

The PI is responsible for coordinating SMC activities and includes the scheduling of meetings and providing appropriate materials to be presented to the SMC. Prior to the first meeting, the PI documents that members do not have conflicts of interest. All discussions and recommendations are summarized and distributed via meeting minutes. The PI develops the SMC meeting agenda, supplies the SMC members with data they require, and verifies reports and recommendations of the SMC.

6.2.2 SMC Responsibilities

The SMC advises the PI on any identified issues and may dictate modification of study procedures if there are concerns with adherence to recruitment protocol, quality and integrity of data collection and data management, and participant safety.

6.2.3 Reports

Within 10 days of each SMC meeting, a report will be prepared by the PI, confirmed by members of the SMC, and submitted to the institution's IRB and the funding agency (NINR) as required by reporting mechanisms. Reporting also includes an annual report to IRB, regulatory and sponsoring agencies as requested, and appropriate reports in the event of an adverse event(s). The SMC is the entity responsible for submitting necessary reports to NINR.

6.3 Description of Data Management

6.3.1 Data Integrity Procedures

The integrity of the intervention and quality of the data will be monitored primarily by the PI, [name], RN, CNM, who is an expert in the safe clinical care of perinatal women.

Random assignment is centrally controlled by our statistician as described in 4.6.1. The Recruiter will obtain informed consent in pregnancy. [name] will train all research team

members with attention to educating members on participants' autonomy, how to avoid applying undue pressure for enrollment, and participants' right to withdraw at any time. All procedures are written, and team members will be required to review written policies.

